Subject Payment. All participants will be compensated for their participation. Participants will be paid \$30 for the initial screening/baseline assessment. They will be compensated \$30 for each medication visit (x7), and \$45 for follow up visits. There will be no payment for therapy sessions. Individuals can receive up to a total of \$330 if attending all scheduled treatment and visits. Payment will be made through electronic funds transfer (EFT). Participants will need to provide us with your banking information by completing a special payment form. Alternatively, if participants do not have a bank account, a check will be mailed to them instead. This check(s) will be mailed to the address they provide us with. Patients may choose to receive gift certificates issued to them for use at the VCS canteen (retail store) or VCS cafeteria here at the VACHS in lieu of EFT/check payment. If a patient chooses to receive payment by gift certificate they will be paid for the telemedicine/telehealth visits they participated in at their next in-person visit (e.g. if they complete weeks 2 and 3 by telephone they will receive gift certificates for weeks 2, 3, and 4 at the week 4 visit). Study payments are subject to withholding for outstanding federal debts (i.e., defaulted student loans, interstate child support, back taxes etc) without notification.

Power analysis: The sample size calculation for our primary hypothesis (change in PTSD symptoms) was based on findings from one of the largest and most comprehensive meta-analysis reports on PTSD treatment to date.[36] The report evaluated N=112 studies and reported on 137 comparisons, using validated PTSD symptom measures. The meta-analysis reported that the *effect sizes* for psychotherapy when contrasted with a control group were consistently large and averaged $g=1.14$. Three studies administered CPT specifically and the overall effect size for those was large and averaged $g=1.69$. For this study we conservatively are basing our calculations on a moderate effect size by Cohen's definition.[95] For the First and Second Primary aim we estimate that with 60 subjects randomized to each group we have 80% power to detect a medium effect size ($f=0.25$) at two-sided alpha level of 0.05, and assuming 25% dropout we will recruit a total of N=160.]

Data Analysis:

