Study data will be collected and managed using REDCap electronic data capture tools hosted at VA CT Healthcare System. REDCap (Research Electronic Data Capture) is a secure, web-based application designed to support data capture for research studies, providing 1) an intuitive interface for validated data entry; 2) audit trails for tracking data manipulation and export procedures; 3) automated export procedures for seamless data downloads to common statistical packages; and 4) procedures for importing data from external sources.

Descriptive statistics and graphs will be used to summarize the data on all randomized subjects. All continuous variables will be examined for adherence to the normal distribution using normal probability plots and Shapiro-Wilk tests. Transformations will be applied if needed. If normality is not satisfied and transformations do not help with achieving normality alternative analytic strategies will be considered such as generalized estimating equations (GEE) or nonparametric methods for repeated measures analysis. Baseline demographic and clinical characteristics for the two randomized groups (e.g., age, gender, severity of PTSD, and opiate use) will be compared using chi-square tests for categorical variables and t-tests or nonparametric tests for continuous variables. If there are baseline differences between study treatment groups, these variables will be used as covariates in the mixed-effects models analyses described below. Drop outs and completers will also be compared on baseline characteristics using the same approach. Between group differences in treatment retention, medication compliance and frequency of the occurrence of side effect symptoms across the treatment period will also be assessed. Residual plots and other diagnostics will be used to assess model assumptions.

The primary analyses will be intent-to-treat but sensitivity analyses on completers and non-completers will also be performed. All statistical testing will be at a two-tailed alpha level of 0.05. *Adjustments for multiple comparisons will be conducted among measures in specific domains. In the case of PTSD symptoms (use of 2 measures, PCL-5 and CAPS-5) and opiate use (use of TLFB and urine toxicology) the level of significance will be adjusted to 0.025.*

Primary and Secondary Hypotheses:

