For the primary and secondary hypotheses, we will use mixed effects models to assess changes in PTSD symptoms and opiate use over time. Treatments will be used as between-subject factors and time (in weeks) will be used as a within-subject factor. The primary outcome variables will be PTSD symptoms as measured by generated from the PCL-5 and CAPS scales. The secondary outcome variables will be frequency of opiate use generated from the TLFB and confirmed with urine toxicology results each medication visit (weeks 1-4, 6, 8, 12) and follow-up. The use of the mixed-effects models approach for the analysis of our longitudinal data has several specific advantages. Unlike traditional repeated measures analyses, mixed effects models allow for different numbers of observations per subject, use all available data on each subject and are unaffected by randomly missing data. They also provide flexibility in modeling the correlation structure of the data.[96]

Primary Aim 1. We hypothesize that CPT will significantly reduce PTSD symptoms compared to IDC in Veterans and civilians with PTSD and comorbid OUD maintained on buprenorphine.

This hypothesis will be tested by the interaction of treatment (CPT vs. IDC), and time in the mixed model specified above. Significantly greater decrease in PTSD symptoms in the CPT group will be considered supportive of the hypothesis.

Secondary Aim 1. We hypothesize that CPT will significantly reduce opioid use compared to IDC in Veterans and civilians with PTSD and comorbid OUD maintained on buprenorphine.

This hypothesis will be tested by the same approach as described in primary aim 1 but with frequency of opioid use as the dependent measure.

Exploratory Hypothesis:

We hypothesize that CPT will significantly improve retention (days in treatment) compared to IDC in Veterans and civilians with PTSD and comorbid OUD maintained on buprenorphine.

This hypothesis will be tested using ANOVA or nonparametric equivalent comparing the two treatment groups (CPT vs. IDC).

We hypothesize that CPT will significantly improve psychosocial functioning (measured by the VR-12 survey) compared to standard counseling in Veterans and civilians with PTSD and comorbid OUD maintained on buprenorphine.

This hypothesis will be tested by the interaction of treatment (CPT vs. IDC) and time.

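### Normality of the raw variables, not of model residuals, governs whether the mixed model is kept, and the loosely specified fallback can bias the treatment effect in either direction when dropout depends on symptoms

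*Combined protocol and SAP*

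**What the plan says.** Under Data Analysis (section 6, Research Plan), the check is on variables: "All continuous variables will be examined for adherence to the normal distribution using normal probability plots and Shapiro-Wilk tests". Transformation comes next where needed. If normality still fails, "alternative analytic strategies will be considered such as generalized estimating equations (GEE) or nonparametric methods for repeated measures analysis". The text does not say whether the check is made by visit, by arm or on pooled data. It gives no significance threshold, and it states no working correlation, weighting or imputation for the fallback. The same section plans residual plots and other model diagnostics, but does not tie them to the choice of model.

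Under Primary and Secondary Hypotheses, the analysis is a mixed-effects model tested by the treatment-by-time interaction. It is used for PCL-5 and CAPS and, by the same approach, for frequency of opioid use. One reason given is that such models "use all available data on each subject and are unaffected by randomly missing data".

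The planned dropout is 25% in the power analysis ("assuming 25% dropout we will recruit a total of N=160") and 30% in the design overview. The general significance level is 0.05, and for the two PTSD measures "the level of significance will be adjusted to 0.025".

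**The concern.** A mixed model assumes roughly normal residuals and random effects. It does not need the raw scores to be normal once visits and arms are pooled. PCL-5 (20 items scored 0–4) and CAPS-5 both run from 0 to 80, and entry requires a PTSD diagnosis on CAPS-5, so raw scores can look non-normal for reasons that do not make the model inadequate. Opioid-use days from the TLFB are likely to contain many zeros.

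Two things are at stake. First, the data influence which primary analysis is run and on what scale, because transforming the outcome changes the quantity estimated. Second, the fallback may be weaker exactly where the mixed model was chosen for its strength. Unweighted GEE is not generally valid when dropout depends on earlier observed outcomes, and nor are rank methods on available cases.

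The protocol makes such dropout foreseeable. It hypothesises better retention on CPT. It says that PTSD is not addressed under IDC and may worsen (Potential Risks, item c). It provides for withdrawal on severe symptomatic deterioration (Protection Against Risk). It also says that CPT may raise symptoms at first (Potential Risks, item b), which could push dropout the other way.

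**Working it through.** **1. The plan's own figures.** The plan gives no figure for the normality check or for dropout by arm. Its power statement supplies the effect size and sample used below: "with 60 subjects randomized to each group we have 80% power to detect a medium effect size", with f = 0.25, which is d = 0.5 for two groups.
- Normal approximation: power = Φ(d·√(n/2) − 1.96) = Φ(0.5·√30 − 1.96) = Φ(0.779) = 0.78. The exact t test gives 0.775. The stated 80% is reproduced approximately.
- Recruitment: 120/(1 − 0.25) = 160, as stated. At the overview's 30% it would be 120/0.70 = 171.4, so 172.

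**2. Can raw scores fail the check?** Shapiro-Wilk at 0.05, 3,000 runs per case. Means and SDs are assumptions, since the documents give none.
- All visits stacked, with random effects and errors exactly normal: 52% rejected. This is the cleanest case of a failed check with an adequate model.
- Baseline truncated at an assumed entry score of 33: 95%.
- Week 12 with a mixture of responders and non-responders: 79%.
- TLFB days with half the values zero: 100%.
- A single week-12 visit with d = 0.5: about 4–5%, no more than the nominal rate.

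The rejection rate therefore depends on how the check is applied, which the plan does not say.

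**3. What the fallback does to the estimate.** Simulation, 1,500 runs per scenario. From the documents: 80 randomised per arm, baseline plus weeks 1, 2, 3, 4, 6, 8 and 12, a 0–80 score, and d = 0.5. Assumed: a random intercept and slope, a week-12 SD of 16.55 (so a true difference of 0.5 × 16.55 = 8.28 points), dropout rates by arm, and dropout depending on the last observed score at 1 logit per SD.

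The estimate is (CPT week 12 − CPT baseline) − (IDC week 12 − IDC baseline). Ratios are to the likelihood mixed model in the same scenario.

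| Dropout IDC / CPT and mechanism | Mixed model | Independence GEE (ratio) | Exchangeable GEE (ratio) |
|---|---|---|---|
| 35% / 15%, unrelated to score | −8.13 | −8.13 (1.00) | −8.12 (1.00) |
| 25% / 25%, worse leave both arms | −8.20 | −8.22 (1.00) | −8.21 (1.00) |
| 33% / 16%, worse leave | −8.24 | −6.28 (0.76) | −7.88 (0.96) |
| 41% / 11%, worse leave | −8.10 | −4.63 (0.57) | −7.47 (0.92) |
| 15% / 33%, worse leave | −8.16 | −10.16 (1.25) | −8.53 (1.05) |
| 33% / 15%, improved leave | −8.15 | −10.18 (1.25) | −8.56 (1.05) |
| 25% / 25%, worse leave IDC, improved leave CPT | −8.24 | −2.80 (0.34) | −7.17 (0.87) |

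**4. Power in the 33% / 16% row**, as Φ(|estimate|/SE − z), with simulated SEs of 2.46, 2.70 and 2.46:
- Mixed model: Φ(8.24/2.46 − 1.96) = 0.92
- Independence GEE: Φ(6.28/2.70 − 1.96) = 0.64
- Exchangeable GEE: Φ(7.88/2.46 − 1.96) = 0.89

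At 0.025 the first two become 0.87 and 0.54 from unrounded values.

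**5. Second simulation** with separately assumed inputs and a true difference of −8.2:
- 29% IDC and 14% CPT dropout among worse patients: likelihood −7.9, independence −6.6 (about 83%; the rounded figures give 6.6/7.9 = 0.835) and exchangeable −7.7 (7.7/7.9 = 0.975).
- Arms reversed: independence −9.4, about 18% above the likelihood model (9.4/8.2 = 1.15 against the true value).
- Equal 23% dropout: all about −8.1.

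**The case against.** The strongest reply is that the plan contains no automatic switch. Variables are examined with plots as well as a test, transformation comes first, and alternatives are only to be considered. A reader might infer that a failed Shapiro-Wilk test forces the change, or that failure at any one of eight visits does, which would occur in 1 − 0.95⁸ = 34% of trials with normal data and independent visits. The text supports neither rule, so none of the rejection rates above is a probability of abandoning the mixed model. This part of the reply stands. What remains is undefined discretion over the primary analysis, exercised after the data are seen and prompted by the wrong diagnostic.

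The second reply is that GEE need not lose much. This also stands in part. With an exchangeable working correlation the error was about 2–8% when dropout rates differed, and 13% when mechanisms were opposite at equal rates. The large errors belong to independence GEE. The plan names neither structure.

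Third, a reader might infer that unequal dropout by itself dilutes the effect. It does not. Unequal dropout unrelated to scores gave no bias, two scenarios inflated the effect, and equal rates with opposite mechanisms diluted it most.

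Fourth, the chart review (10/10 retained against 11/36) is tempting as a forecast of dropout by arm. It compares patients referred or not referred to trauma-focused therapy, without randomisation, and is not CPT against IDC.

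Finally, residual diagnostics are already planned. That makes the remedy easier but does not supply it, because they do not govern the choice of model.

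**Conclusion.** The concern holds in a limited form and should be fixed. The plan looks at raw variables where it should look at residuals, and it permits a data-dependent move to a different scale or method without stating the trigger or how missing data would then be handled. That move can give up the stated missing-data reason for the mixed model.

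Under the assumed inputs, independence GEE recovers about 76–83% of the effect at roughly 29–33% IDC and 14–16% CPT dropout with worse patients leaving. It overstates the effect by about 18–25% with the arms reversed. It is about unbiased when rates and mechanism are the same in both arms. Exchangeable GEE is off by only about 2–8% when rates differ. A general claim of attenuation, or of certain loss of protection, is not supported.

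The sizes rest on assumed means, SDs, dropout rates and dropout slope, and on dropout that depends only on observed scores. The simulated visits follow the PCL-5 schedule. CAPS-5 is collected before and after treatment and at follow-up, and was not simulated separately. Rank methods were not simulated. The dropout runs used roughly normal scores, so they show the cost of leaving the mixed model when it is adequate, not its behaviour under severe non-normality.

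**What to change.** - **PCL-5 and CAPS-5:** state that the likelihood mixed model on the untransformed scale is the primary analysis whatever a Shapiro-Wilk test on raw scores shows. Judge adequacy with the residual diagnostics already planned. If residuals are clearly non-normal, keep the model and use robust or bootstrap standard errors.
- **GEE:** restrict it to a sensitivity analysis, with a named working correlation and either inverse-probability-of-dropout weights or multiple imputation.
- **TLFB opioid-use days:** pre-specify a likelihood-based generalised linear mixed model for counts or proportions that suits many zeros. A normal model is a poor starting point there, so a switch triggered by non-normality is the wrong device.

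The cost is SAP wording and minor extra analysis. No change to design, visits or sample size is needed.

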 - a. Attempt to schedule study visits on the same day as another clinic visit the patient has scheduled.
 - b. As much as possible, self-assessment forms should be completed via telephone or telemedicine and can be given directly or mailed to the participant in advance of any appointment. If the patient desires to complete in-person visit forms on site, staff will honor that request while maintaining social distancing.
 - c. Study therapy sessions (CPT or IDC) will be allowed to be conducted as telemedicine visits using VA approved platforms (e.g. VA Video Connect or VVC). If a video option is not possible, therapy can be conducted over the phone or in person (patient's choice).
 - d. Scheduled in-person visits at weeks 2, 3, 6, and the two follow-up visits (months 1 and 3) will now be conducted by telephone or telemedicine.

(a) **Clinician Administered PTSD Scale (CAPS-5)** will be used to diagnose PTSD and to obtain data [(pre and post treatment, follow-up)] on the frequency and severity of PTSD symptoms. The CAPS-5 is a structured diagnostic interview for DSM-5 diagnosis and the gold standard for assessing PTSD. It has excellent psychometric properties and diagnostic efficiency.[82] The CAPS for DSM-5[83] uses only a single 5-point ordinal rating scale to measure symptom severity. CAPS-5 scores range from 0 to 80 with higher scores indicating greater PTSD symptom severity. The CAPS-5 was revised with an eye towards maintaining backwards compatibility with the DSM-IV version of the instrument.

(b) **PCL-5** will be used to collect information on PTSD symptoms. The PTSD Checklist for DSM-5 [83] is similar in form to the PTSD Checklist (PCL) based on the DSM-IV.[84] The PCL-IV has excellent psychometric characteristics. The PCL-5 is a 20-item self-report measure, selected for its dimensional sensitivity, with higher scores reflecting greater PTSD severity. Scoring is based on how much the patient has been bothered by the symptoms on a scale from “0 = not at all” to “4 = extremely.” PCL scores will be collected based upon symptoms experienced in the past month at baseline, but since the last visit, during the weekly assessments.

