day as needed for stabilization of opioid withdrawal symptoms, within a 5-7-day period, which is standard practice. At the end of the active study, participants will be referred to a buprenorphine clinic.].

Common side effects of buprenorphine/naloxone, which are similar to other opioids, include: abdominal pain, constipation, nausea, vomiting, headache, sweating, sedation, and allergic reaction. Uncommon but more serious adverse effects of BUP/NLX include liver enzyme and/or hepatic abnormalities, orthostatic hypotension, and respiratory depression. There is also a risk of unintentional exposure, especially with children, so for that reason participants will be educated to keep their medication in a safe place to prevent unintentional exposure to others. Buprenorphine is a Schedule III drug and is generally well tolerated, although it does cause a physiologic addiction and may lead to withdrawal effects if discontinued abruptly. *Buprenorphine/Naloxone detoxification:* detoxification from BUP/NLX can produce signs and symptoms of opiate withdrawal including: nasal congestion, abdominal symptoms, anxiety, myalgia, insomnia, sweating, and diarrhea.

b) Subjects who are randomized to *Cognitive Processing Therapy (CPT)* will receive 12 weeks of therapy by a licensed provider. CPT may produce some discomfort and/or emotional upset including an initial increase of PTSD symptoms due to the discussion of traumatic events. This is likely to happen during the early sessions of therapy as the participant begins to describe his/her experiences, thoughts, images and feelings to the therapist as well as during the evaluations. However, these experiences are believed to be an important part of the treatment and recovery process. Dealing effectively with emotional upset means experiencing the negative emotion in order to learn to handle it in future instances. Concerns have been expressed about the safety of CPT, particularly the concern that some individuals may find the treatment overwhelming and cause an increase in symptoms or further deterioration in functioning. These concerns are based primarily on unsystematic clinical impression and research does not support such concerns.

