Following the baseline assessment, participants who meet the inclusion criteria for the study will be randomized into the study. For individuals not meeting study inclusion criteria, the study staff will provide options for follow-up outside of the study.

- **Protection Against Risk:**

- *General procedures to protect against risks:* Before initiating any research activity, each subject must give informed consent that will detail the risks of study participation. Eligibility will be determined by the medical and psychiatric history, drug use history, and the laboratory studies done prior to beginning this research protocol. Subjects will be provided a number to call to reach an on-call psychiatrist (24 hours/day) should unpleasant effects occur after subjects have left the testing facility.
- *Protection against adverse events from buprenorphine maintenance:* Subjects will be monitored carefully for the development of adverse side effects (including symptoms of withdrawal) during the study. Subjects will be withdrawn if they show severe psychological or symptomatic deterioration or if clinically necessary for ethical or safety purposes. Any psychiatric hospitalization will be reported to the Principal Investigator for review regarding the appropriateness for continuation in the study. Similarly, medical complications will be reviewed in the manner described above. Subjects who may no longer participate for these reasons, or who choose to terminate from the study, will be offered treatment at the VA according to the individual's needs. If a subject shows clinical deterioration the PI will determine: 1) whether the subject can remain in the study, or; 2) whether a higher level of care (e.g. referral back to treating psychiatrist or referral to emergency or inpatient care) is needed.

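### Participants withdrawn for severe deterioration have no planned later assessment, so outcome-related missing data enter a mixed model that relies on random missingness

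*Combined protocol and SAP*

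**What the plan says.** All places are in section 6 (Research Plan) of the combined protocol and SAP.

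- **Withdrawal rule** (Protection Against Risk): "Subjects will be withdrawn if they show severe psychological or symptomatic deterioration or if clinically necessary for ethical or safety purposes". Also: "Any psychiatric hospitalization will be reported to the Principal Investigator for review regarding the appropriateness for continuation in the study". For clinical deterioration in general, the principal investigator decides whether the person stays in the study or needs a higher level of care. "Subjects who may no longer participate for these reasons" are offered VA treatment. No study assessment after that point is described.
- **Risk of worsening** (Potential Risks): item (b) expects some initial symptom increase with CPT and adds "This is likely to happen during the early sessions of therapy". Item (c) says PTSD is not addressed in IDC and may worsen.
- **Measurement** (Study Assessments): CAPS-5 is taken "pre and post treatment, follow-up". In Table 1 as extracted, its first mark after baseline is at week 8. PCL-5 and TLFB are marked at weeks 1 to 4, 6 and 8.
- **Analysis** (Data Analysis; Primary and Secondary Hypotheses): intent-to-treat mixed models, chosen because they "use all available data on each subject and are unaffected by randomly missing data". Sensitivity analyses on completers and on non-completers are planned, as is a baseline comparison of dropouts with completers.
- **Safety by arm** (Data Analysis): retention, medication compliance and "frequency of the occurrence of side effect symptoms across the treatment period will also be assessed". SAEs go to the IRB, the DSMB and other authorities. C-SSRS is collected through both follow-ups, with no stated analysis.

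**The concern.** Withdrawal for severe deterioration depends on the outcome itself. If assessment ends there, the worst courses drop out of the comparison, and the model fills the gap as if those people had gone on like similar participants who stayed.

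CAPS-5 is the more exposed measure. Someone withdrawn in the early weeks has no CAPS-5 value after baseline, so nothing in the CAPS-5 data carries the deterioration into the model. Calling the analysis intent-to-treat does not supply the missing values.

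The other planned analyses do not close the gap. A completer analysis drops these participants. A non-completer analysis has only their early data. A baseline comparison cannot show worsening after baseline. Days in treatment counts the loss but not its cause.

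At stake is the contrast on a primary outcome. The Significance section adds that safety and effectiveness in this population cannot be assumed and must be shown by trials.

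**Working it through.** **1. The plan's own figure.** Power analysis: f = 0.25 (for two groups d = 2f = 0.5), 60 per arm, two-sided alpha 0.05. Normal approximation: Φ(0.5 × √(60/2) − 1.96) = Φ(0.779) = 78.2%, within 2 points of the stated 80%. Inflation: 120/(1 − 0.25) = 160, or 80 per arm. The yardstick for any bias is therefore 0.5 SD.

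**2. CAPS-5.** Let q be the share of an arm withdrawn for deterioration before its first CAPS-5 after baseline, and g how much worse (in SD) their end-of-treatment score would be than that of the rest of their arm. The full arm mean is m + qg. A model that assumes random missingness estimates about m. So

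shift in contrast = (q in one arm − q in the other) × g, in favour of the arm with the larger q.

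The documents give neither q nor g. Assumed values, for an excess in either arm:

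| Excess | g = 1 SD | g = 2 SD |
|---|---|---|
| 0% | 0 | 0 |
| 5% (4 of 80) | 0.05 | 0.10 |
| 10% (8 of 80) | 0.10 | 0.20 |

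Against 0.5 SD, the largest entry is 0.20/0.5 = 40%, upward or downward, and the smallest is zero. A simulation (80 per arm, baseline-adjusted, 25% random dropout, excess placed in CPT) agrees. The effect with everyone followed against the effect as planned is −0.448 against −0.499 (5%, 1 SD; shift 0.051) and −0.306 against −0.507 (10%, 2 SD; shift 0.201). An excess in IDC reverses the sign.

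**3. PCL-5.** Values before withdrawal stay in the model and pull the estimate towards the truth. With an assumed covariance (intercept SD 0.8, slope SD 0.04 per week, residual SD 0.6), visits at weeks 0, 1, 2, 3, 4, 6, 8 and 12, and withdrawal after week 2 or 4, the shift runs from 0.017 SD (5%, 1 SD, week 4) to 0.099 SD (10%, 2 SD, week 2). This supposes that the worsening shows in PCL-5 before withdrawal. If it shows only in part, the shift moves towards the CAPS-5 figure.

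**4. Would the retention test reveal it?** The plan states "We hypothesize that CPT will significantly improve retention (days in treatment) compared to IDC", tested on days in treatment for any cause. With 84 days, 80 per arm, 25% other dropout and deterioration withdrawals on days 14 to 49, an excess of 5% to 10% is detected with about 9% to 23% power. A detected difference would still not show the reason.

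**The case against.** **No sentence says that assessment stops at withdrawal.** This is true, and the data loss is an inference. The withdrawal sentence also stands under a heading on buprenorphine adverse events, and the parallel paragraph on CPT and IDC distress speaks of monitoring and referral, not withdrawal. But the wording covers any severe psychological deterioration, describes leaving the study rather than the therapy, and is followed by no assessment plan. If the sponsor does intend follow-up, one sentence settles it.

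**The direction is open.** This stands in full. A reader might infer from the passage on early symptom increase that the bias flatters CPT. The documents do not support that: the same passage says research does not bear out the concern about deterioration, and the IDC passage names worsening PTSD as a risk of the control. The small local data (CPT well tolerated in a pilot; 10 of 10 retained after referral to trauma-focused therapy in a chart review) do not point to excess loss under CPT either.

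**PCL-5 is protected in part.** This stands. Primary Aim 1 names PCL-5 as the measure, confirmed by CAPS-5. If withdrawal follows worsening already recorded on PCL-5, the model's assumption may largely hold for that scale. CAPS-5 is nevertheless listed as a primary outcome variable and lacks this protection.

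**Safety is overseen.** The DSMB receives adverse events quarterly, and discontinuation parameters are to be proposed to it before the study starts. That protects participants, but it is not a stated comparison by arm in the results. Alone, the missing table would be close to a reporting preference.

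**Conclusion.** The point holds as a cheap improvement. Followed as written, the plan creates outcome-related missing data in its primary comparison and has no analysis that addresses it. On assumed values (excess 0% to 10% in either arm, outcome 1 to 2 SD worse), the CAPS-5 contrast moves by 0 to 0.20 SD in either direction and PCL-5 by up to about 0.10 SD. These figures illustrate; they do not estimate anything in this trial.

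Two stronger conclusions are tempting and should not be drawn. One is that the trial will overstate CPT by some fixed share of its planned effect: that needs an excess of withdrawals in CPT, which nothing in the documents establishes. The other is that harm would go unseen: side effects are compared by arm during treatment, and PTSD symptoms, opioid use and treatment utilization are compared by arm to 3 months among those still assessed. A large CPT effect would also survive shifts of this size.

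**What to change.** Amend Protection Against Risk, with a matching line in Data Analysis:

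> Participants withdrawn from study therapy remain in assessment unless they withdraw consent. CAPS-5, PCL-5, TLFB and C-SSRS are done at withdrawal and at the scheduled end-of-treatment, 1-month and 3-month visits, and these data are included in the intent-to-treat models.

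As a secondary addition, keep the side-effect comparison and tabulate SAEs, C-SSRS events and withdrawals for deterioration by randomised arm, separately for treatment and follow-up, descriptively and with numbers assessed. Note under the table that IDC participants may take up CPT after the study.

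Cost: the instruments exist and the follow-ups are already by telephone or telemedicine. Each participant withdrawn early needs up to four assessments that the plan does not now describe (withdrawal, end of treatment, 1 month, 3 months). At the protocol's rates, taking the first two as medication visits, payments are at most 2 × 30 + 2 × 45 = 150 dollars each. Some deteriorated participants will decline, so the bias is reduced, not removed. The table will be imprecise: for 12.5% against 2.5%, the 95% CI half-width is about 8 percentage points with 80 per arm and 9 with 60.
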